Proposal

Serum thromboxane B2 Assay as a Measure of Platelet Production in Healthy Volunteers

Taking Aspirin

Short study name: COX-1 and TxB2

Principal Investigator: [name]

Laboratory Investigator: [name],

Co-investigators: [name], [name]^{1,2,3}, [name]^{1,2}, [name], [name]^{2,3}, [name].

Affiliations:

¹ Thrombosis and Atherosclerosis Research Institute (TaARI),

² Department of Medicine, McMaster University

³ Population Health Research Institute, Hamilton Health Sciences McMaster University

Overall objective:

To develop a valid method to quantify platelet production (without the use of radioactive isotopes) in order to examine the hypothesis that enhanced platelet production is a common cause of poor aspirin responsiveness in patients with atherothrombosis.

Specific objective:

To validate the Cayman Chemical serum thromboxane immunoassay as a measure of platelet production in healthy subjects who are treated with aspirin by demonstrating that the recovery of their serum thromboxane B2 levels occurs at a rate of about 10% per day after aspirin cessation.

Background and Rationale:

Cardiovascular disease is the most common cause of preventable death globally. Given once-daily, low dose aspirin reduces the risk of major cardiovascular events (MACE) by 25% in patients with atherothrombosis¹. By irreversibly acetylating cyclooxygenase-1 (COX-1) in platelets, aspirin blocks the production of thromboxane (TX) A₂, a potent stimulator of platelet aggregation, thereby mediating its anti-thrombotic effect. Despite its rapid clearance (30 minutes) from the circulation, the effect of aspirin on the inhibition of TXA₂ synthesis lasts for the lifespan of the platelet, which is about 10 days². In healthy subjects, a single 100-mg dose of aspirin inhibits almost 100 percent of TXA₂ synthesis within 30 to 60 minutes of its administration. TXA₂ synthesis then recovers slowly as the aspirin is cleared and new platelets with non-acetylated COX-1 ('unacetylated' platelets) are released from the bone marrow. Since only about 10% of platelets

Serum thromboxane B2 and platelet production

are replaced daily by new platelets entering the circulation, at 24 hours after a dose of aspirin, TXA₂ synthesis is still suppressed by > 90%. At this level of suppression, TXA₂ mediated platelet aggregation remains maximally inhibited. So, provided that no more than 10% of 'unacetylated' platelets enter the circulation per day, once daily aspirin maintains an optimal antithrombotic effect.

Soon after aspirin was shown to be effective as an antithrombotic agent, several investigators reported that unlike healthy subjects, about a third of patients treated with aspirin showed incomplete suppression of TX synthesis or arachidonate-induced platelet aggregation³. These patients were called poor responders and subsequent studies showed that poor response to once daily aspirin, identified by either TX or by platelet aggregation assays, was associated with reduced antithrombotic effectiveness⁴. Several groups, including ours, proposed that, in certain conditions (e.g. post-coronary artery bypass grafting⁵, diabetes⁶, and essential thrombocythemia⁷), poor response to aspirin was caused by an increased rate of platelet production. Such a mechanism is a plausible cause of poor response to aspirin because an increased rate of platelet production would result in an increased proportion of 'unacetylated' platelets entering the circulation after aspirin is cleared, which would shorten the duration of platelet COX-1 suppression to <24 h. Because full suppression of TXA₂-dependent platelet function requires >90% inhibition of COX-1 activity, even a modest recovery of this activity can sustain a substantial platelet response⁸. Consistent with this proposed mechanism, we and others showed that a poor response to aspirin was reversed by giving aspirin twice daily (instead of once)^{6,7}. It is possible that an increased rate of platelet production is responsible for most cases

of poor response, in which case, the response could be restored by twice daily aspirin administration. Our ultimate aim is to test this hypothesis, but to achieve this aim we need to develop an accurate test of platelet production to identify patient groups that would benefit from twice daily aspirin.

How can we identify patients in whom an increased rate of platelet production is responsible for poor response to aspirin? Previous methods to measure platelet production in healthy subjects, which were based on survival of radiolabeled platelets, have shown that platelets survive in the circulation for about 10 days. The **specific objective** of this study is to demonstrate that in healthy subjects in whom production of new platelets occurs at rate of 10% per day, the recovery of serum thromboxane B2 per day would be about 10%. Instead of labeling with radioactive isotopes, we will use the acetylation of platelet COX-1 by aspirin to identify the rate of platelet production. Our method is based on the observation that in normal subjects, after a single dose of aspirin, unacetylated COX-1 recovers at a rate of about 10 percent per day as new platelets enter the circulation⁹. However, measuring acetylation status of protein requires specialized proteomics assays. Instead, we intend to use an assay to quantify serum TXB2 as an indirect measure of the effect of unacetylated COX-1 from new platelets. If true, then the daily recovery of serum TXB2 would provide a readout of new platelet production.

The serum thromboxane B2 method has the additional advantage of providing information on both the rate of platelet production and the degree of platelet inhibition by aspirin. Such an advantage would facilitate the identification of non-responders whose reduced response is due

Serum thromboxane B2 and platelet production

to an increased rate of platelet production, as well as the assessment of response following aspirin dose modification in future studies.

Implications of this study:

Successful validation of serum thromboxane B2 assay performed in-house as a measure of platelet production will be critical to pursuing our multistep research program to: 1) investigate the frequency with which increased platelet production results in poor response to aspirin; 2) identify patient populations in whom increased production is a major cause of poor response to aspirin; 3) test the hypothesis that poor response in those populations can be overcome by twice daily aspirin; and 4) evaluate the effect of twice daily aspirin in those populations on reducing the risk of cardiovascular events.

Methods:

Study design: Healthy volunteers will take aspirin 81 mg daily for 5 days. Serum thromboxane B2 (sTxB2) will be measured before taking aspirin (baseline), at 4h after last dosing (daily peak level), and then daily for 5 days after aspirin cessation.

Population: 20 healthy volunteers. Enrollment criteria are listed below:

- Inclusion criteria:
 - Healthy non-smoking volunteers;
 - Age \geq 18 years;
- Exclusion criteria:

Serum thromboxane B2 and platelet production

- Allergy or intolerance to aspirin;
- Current pregnancy;
- Use of aspirin or drugs interfering with platelet function (NSAIDs, anticoagulants) within one week of study enrolment.

Assays:

- Serum Thromboxane B2: serum TXB2 concentrations were measured using an enzyme immunoassay kit (Cayman Chemical, Ann Arbor, MI) according to the instructions provided by the manufacturer. In-house controls were tested with each batch.

Blood collection: 2.5 ml of blood in a serum tube for sTxB2 assay, and 3 ml of blood in EDTA for platelet count at baseline.

Statistical considerations:

- Sample size: As a pilot study, we plan to enroll 20 patients as recruitment of this number is feasible. This study will provide estimates of mean/median and variability (e.g. standard deviation and range) of serum thromboxane B2 and recovery in healthy volunteers and will inform on sample size calculation of future studies with this assay.
- Proposed analyses:
 - Biological variability of serum TXB2 will be represented as mean/median and standard deviation/range, at each time point of sampling.

Serum thromboxane B2 and platelet production

- Residual serum TXB2 will be plotted against time and recovery rate of serum TXB2 will be estimated, and compared with 10% rate of new platelet production reported in historic studies using radiolabeling method for detection.

Anticipated result:

In healthy subjects in whom production of new platelets occurs at rate of 10% per day, we expect a 10% increase in serum thromboxane B2 per day;

Study coordination, recruitment and logistics

This study will be performed at PHRI & TaARI. Healthy volunteers will be screened and recruited by the investigators or research assistants. Informed consent will be obtained from participants before we conduct our study. Samples will be collected by our research assistant or investigators and then transferred to TaARI for testing.

Role of the principal investigator

[name] is the principal investigator, and will have lead roles in study oversight, protocol development, Research Ethics Board submission, creation of database, develop the detailed statistical analysis plan, and draft the manuscript for reporting study results.

[figure not shown]
Ethical considerations:

We will ensure that each participant fully understands the purpose and procedures of this study. Written informed consent will be obtained from each participant. The risk of aspirin is

Serum thromboxane B2 and platelet production

well documented, and unforeseeable risk limited. We will keep in close contact with the participants for the 2 weeks of study. Participant data will only be used for the purpose of the study. We will ensure confidentiality by storing data in a keyword-secured computer in an ID badge-secured building and restricting data access to research personnel only.

Figure 1. Study procedure

* ASA, acetylsalicylic acid; sTx2, serum thromboxane B2; ICF, informed consent form.

References:

- 1 Antithrombotic Trialists, C. Collaborative meta-analysis of randomised trials of antiplatelet therapy for prevention of death, myocardial infarction, and stroke in high risk patients. *BMJ* **324**, 71-86 (2002).
- 3 Campbell, C. L. & Steinhubl, S. R. Variability in response to aspirin: do we understand the clinical relevance? *J Thromb Haemost* **3**, 665-669, doi:10.1111/j.1538-7836.2005.01119.x (2005).

4 Hankey, G. J. & Eikelboom, J. W. Aspirin resistance. *Lancet* **367**, 606-617, doi:10.1016/S0140-6736(06)68040-9 (2006).

5 Paikin, J. S. *et al.* Multiple daily doses of acetyl-salicylic acid (ASA) overcome reduced platelet response to once-daily ASA after coronary artery bypass graft surgery: a pilot randomized controlled trial. *J Thromb Haemost* **13**, 448-456, doi:10.1111/jth.12832 (2015).

6 Rocca, B. *et al.* The recovery of platelet cyclooxygenase activity explains interindividual variability in responsiveness to low-dose aspirin in patients with and without diabetes. *J Thromb Haemost* **10**, 1220-1230, doi:10.1111/j.1538-7836.2012.04723.x (2012).

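### Is one pre-aspirin thromboxane sample too few to anchor the percent-recovery rates?

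*Protocol*

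**What the plan says.** The Study design paragraph of the protocol places one sTxB2 measurement before aspirin ("Serum thromboxane B2 (sTxB2) will be measured before taking aspirin (baseline") and the others "at 4h after last dosing (daily peak level), and then daily for 5 days after aspirin cessation". The text therefore shows seven sTxB2 time points: one uninhibited and six under or after aspirin. Figure 1, which sets out the study procedure, is not available in the copy reviewed.

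The Background states that radiolabelling studies "have shown that platelets survive in the circulation for about 10 days". Under Anticipated result the protocol says "we expect a 10% increase in serum thromboxane B2 per day". Under Proposed analyses the "recovery rate of serum TXB2 will be estimated, and compared with 10% rate of new platelet production". The Sample size paragraph sets 20 participants on grounds of feasibility and promises "estimates of mean/median and variability (e.g. standard deviation and range) of serum thromboxane B2 and recovery in healthy volunteers" as input to the sizing of later studies. It gives no power, margin or confidence-interval width. Nor does the protocol state a within-person CV for the assay, a between-person SD of the recovery rate, or the denominator of that rate.

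**The concern.** A recovery rate can be compared with 10% platelet replacement per day only if it is a share of the uninhibited level, and the natural reference is the participant's own baseline. Sampling ends 5 days after cessation, when recovery should be about half complete, so no later sample can act as a second reference. Day-to-day and assay error in the one baseline then multiplies all of that person's percentages, and further follow-up samples do not average it out.

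The SD and range of recovery are a stated product of the pilot, and baseline error widens both. A sample that was never drawn cannot be supplied by a later analysis plan. The remedy looks cheap: one more 2.5 ml tube per person, in a study that already expects two weeks of contact.

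**Working it through.** **Inputs from the protocol.** Recovery 10% per day; five daily samples after cessation; 20 participants; 2.5 ml per sTxB2 tube and 3 ml EDTA at baseline. The 20 rests on feasibility, so there is no sample-size calculation to reproduce.

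**Inputs that must be assumed.** Within-person CV of one sTxB2 value (5 to 30%); SD of true rates between people (2 points per day, and 3 as a variation); equal CV at all samples; independent errors; rate = least-squares slope over days 1 to 5 divided by own baseline.

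**Is there a second reference?** 5 days × 10% = 50%. No later sample is expected near 100%, so this part of the concern is correct.

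**Approximate variance of an individual rate with m baselines:**

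Var ≈ 2² + 1.24 × (10² + 2²) × CV² + (10 × CV)²/m

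The factor 1.24 is the sum over t = 1 to 5 of [(t − 3) × t]², divided by 10²: (4 + 4 + 0 + 16 + 100)/100.

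At CV 10%: 4 + 1.29 + 1.00 = 6.29 with one baseline (SD 2.51), and 4 + 1.29 + 0.50 = 5.79 with two (SD 2.41), a fall of about 4%. The approximation understates the effect at high CVs, so the table uses simulation (1,000,000 participants, lognormal errors). Equivalent n = 20/(1 − fall)²; CI half-width = 2.093 × SD/√20.

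| CV | SD, one baseline | SD, two | Fall | Equivalent n | 95% CI half-width, one / two |
|---|---|---|---|---|---|
| 10% | 2.54 | 2.42 | 4.7% | 22.0 | 1.19 / 1.13 |
| 15% | 3.12 | 2.88 | 7.7% | 23.5 | 1.46 / 1.35 |
| 20% | 3.81 | 3.43 | 10.1% | 24.7 | 1.78 / 1.61 |
| 25% | 4.64 | 4.07 | 12.3% | 26.0 | 2.17 / 1.90 |
| 30% | 5.56 | 4.77 | 14.3% | 27.2 | 2.60 / 2.23 |

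At CV 5% the fall is 1.6%, equivalent to 20/0.984² = 20.7 participants. With a true SD of 3 and CV 10% it is 2.9%.

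**Independence.** Error common to all of a participant's samples, such as one assay batch or a personal shift lasting the study period, cancels in the ratio. If half the error variance is shared in this way, the fall at CV 15 to 30% is about 5 to 11% (equivalent n 20/0.95² = 22.2 to 20/0.89² = 25.2). If only the two baselines correlate, at 0.5, it is about 4 to 7% (20/0.96² = 21.7 to 20/0.93² = 23.1).

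**Bias of the mean.** Averaging individual ratios arithmetically multiplies the mean by about 1 + CV²: 10 × 1.0225 = 10.2 at CV 15% and 10 × 1.09 = 10.9 at CV 30%. The protocol does not prescribe that estimator, and a ratio of means avoids most of the bias. It is a matter of analysis, not of sampling.

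**Cost.** Blood volume rises from 7 × 2.5 + 3 = 20.5 ml to 8 × 2.5 + 3 = 23.0 ml. A second tube from the same draw would reduce only assay and handling error. The full gain needs another pre-aspirin day.

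**The case for a change.** The best argument for the concern is that it affects a stated product. The pilot is to report the variability of recovery, and with one sample per time point that SD mixes true differences between people with day-to-day and assay error. A baseline pair would separate the two without assuming linear recovery or equal CV at suppressed levels. At a CV of 25 to 30%, baseline error would make up 44 to 50% of the variance of individual rates under independence, and a second baseline would be worth about 6 or 7 extra participants. The Ethical considerations section says "We will keep in close contact with the participants for the 2 weeks of study", while 5 dosing days and 5 follow-up days fill about 10 of 14, so an extra day may fit.

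The mechanism and the arithmetic stand. The conclusion that the plan is deficient does not follow:

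- The protocol promises the SD of recovery, and one baseline delivers it. If later studies also use one baseline, that wider SD is the right planning input. What is lost is a direct estimate of what a two-baseline design would save, which the protocol does not promise.
- The separation would itself be rough. At a true CV of 25%, 95% of estimates from 20 pairs lie between 17% and 33%.
- The two-week statement concerns contact, not visits, and nothing in the text shows that consent and baseline fall on different days.
- The text never says that the baseline is a single draw. It gives no sign of a repeat, but without Figure 1 one cannot be excluded.

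**Conclusion.** The concern does not hold. The protocol states nothing wrongly here and does not contradict itself, and one pre-treatment sample is an ordinary choice for a feasibility pilot of 20 with no precision target. The possible gain in the SD of individual rates runs from 1.6% (CV 5%) to 14% (CV 30%) with a true SD of 2 and independent errors. At CV 15 to 30% it shrinks to about 5 to 11% or 4 to 7% under the two correlation patterns tried. All of these figures depend on a CV, a between-person SD, an error structure and a denominator that the protocol does not give. Against them stands an extra venepuncture on a separate day for each volunteer, which reasonable statisticians could decline. A second baseline would be a sensible option if the within-person CV proved high and the errors largely independent. Its absence is not a fault in the plan, and no change is required.

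### The one-week aspirin exclusion is shorter than the roughly 10-day aspirin effect stated in the protocol, so it does not ensure an unsuppressed baseline sTxB2

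*Protocol*

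**What the plan says.** Under Methods, Population, the protocol's exclusion criteria list "Use of aspirin or drugs interfering with platelet function (NSAIDs, anticoagulants) within one week of study enrolment". The window is one week, and it is counted from enrolment.

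Background and Rationale gives the duration of the effect that this criterion guards against. The inhibition of thromboxane synthesis "lasts for the lifespan of the platelet, which is about 10 days". Radiolabelling studies "have shown that platelets survive in the circulation for about 10 days". After a single dose, "unacetylated COX-1 recovers at a rate of about 10 percent per day as new platelets enter the circulation".

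Under Study design, sTxB2 "will be measured before taking aspirin (baseline), at 4h after last dosing (daily peak level), and then daily for 5 days after aspirin cessation". There is therefore one pre-aspirin sample per volunteer.

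Under Proposed analyses, "Biological variability of serum TXB2 will be represented as mean/median and standard deviation/range, at each time point of sampling". A recovery rate is also to be estimated and compared with 10%. The text does not say whether residual sTxB2 or recovery is scaled to baseline.

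On timing, Ethical considerations says "We will keep in close contact with the participants for the 2 weeks of study". The interval from enrolment to the baseline sample is not given in the text. Figure 1, captioned as the study procedure, may give it but is not available.

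**The concern.** The criterion is there to keep residual aspirin effect out of the study, yet it is about 3 days shorter than the effect as the protocol describes it. Chronic use is not needed for it to fail: Background and Rationale says that one 100-mg dose inhibits almost all thromboxane synthesis in healthy subjects. A volunteer who took a single tablet just outside the window could be enrolled with thromboxane synthesis still partly suppressed.

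Two planned outputs are exposed. The first is the description of baseline sTxB2, which takes in the low value however recovery is defined. The second is the recovery rate, but only if it is expressed as a share of baseline; too small a denominator then makes recovery look too fast. That rate is what the study sets against 10% per day. Later analysis cannot restore a baseline that was drawn while suppressed.

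**Working it through.** **Inputs from the protocol**
- Exclusion window: one week before enrolment (Methods, exclusion criteria).
- Duration of effect and platelet lifespan: about 10 days (Background and Rationale).
- Recovery: about 10% per day (Background and Rationale).
- Sample size: 20, chosen for feasibility (Statistical considerations).
- Schedule: 5 dosing days, 5 daily samples after cessation, 2 weeks in all (Study design; Ethical considerations).

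**Assumptions, not in the protocol**
- Recovery is linear in time.
- The number of affected volunteers is 1 to 4 of 20.
- The gap from enrolment to baseline is 0 unless stated.

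**Step 1. Reproduce the protocol's own rate.** 1 / 10 days = 10% per day. The stated lifespan and the stated rate agree.

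**Step 2. Baseline as a fraction of true.** With last aspirin d days before the baseline sample, f(d) = min(1, 0.10 × d). If recovery is expressed relative to baseline, a true 10% per day reads as 10 / f(d).

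| Last aspirin before baseline | Baseline, % of true | Apparent recovery if relative to baseline, %/day |
|---|---|---|
| 7 days (only if day 7 is eligible) | 70 | 10 / 0.70 = 14.3 |
| 8 days | 80 | 10 / 0.80 = 12.5 |
| 9 days | 90 | 10 / 0.90 = 11.1 |
| 10 days or more | 100 | 10.0 |

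**Step 3. Group effect with k of 20 affected at day 8, all with a true rate of 10% per day.**
- Baseline mean as a fraction of true = ((20 − k) + 0.8k) / 20. This is 0.99 for k = 1, 0.98 for k = 2 and 0.96 for k = 4.
- Mean recovery relative to baseline = ((20 − k) × 10 + k × 12.5) / 20. This is 10.1 for k = 1 (10.125 before rounding), 10.25 for k = 2 and 10.5 for k = 4.
- If day 7 is read as eligible and all affected volunteers are at day 7, ((20 − k) × 10 + k × 14.286) / 20 gives 10.2, 10.4 and 10.9 for k = 1, 2 and 4.
- Under this model the median recovery stays at 10.0, because at most 4 of 20 values move.

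**Step 4. What a gap between enrolment and baseline would do.** With a gap of g days, d is the days from last aspirin to enrolment plus g. For last aspirin 7 days before enrolment, gaps of 0, 1, 2 and 3 days give baseline fractions of 70, 80, 90 and 100%. For last aspirin 8 days before enrolment, 2 days is enough. The schedule has room: 5 + 5 = 10 of 14 days are used, which leaves up to about 4.

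**Step 5. Sensitivity to the linear assumption.** If turnover were geometric, 1 − 0.9^d, the recovered share would be 57% at day 8 and 61% at day 9, and a 3-day gap would not close the shortfall. The linear form is used here because it matches a fixed lifespan of about 10 days and gives the smaller effect.

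**The case against.** Several objections have force.

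- **Figure 1 is not available.** It may place consent, baseline and dosing in time, and a gap of about 3 days would remove the effect on the linear model. A reader might infer that counting from enrolment is a defect in itself. The available text does not show that, because content lost with a figure cannot be counted as missing from the plan. What stands is the mismatch of one week against about 10 days.
- **Day 7 is a boundary.** Use exactly 7 days before enrolment is arguably within one week and so already excluded. The first clearly eligible whole day is then day 8. For this reason the size is stated at day 8, with day 7 only as a conditional case.
- **Scaling is not fixed in the text.** The protocol refers to a detailed statistical analysis plan, which is not available and may define recovery and residual sTxB2. A reader might infer that the recovery estimate is biased. That follows only if recovery is relative to baseline. In concentration units the slope is untouched, because the five days of study aspirin suppress synthesis afresh; of the seven sampling times, only baseline is affected.
- **A single volunteer's result.** If recovery is linear at a person's own rate r and baseline is still suppressed, the baseline-relative reading is r / (r × d) = 1/d, which no longer depends on r. A reader might infer that the assay then says nothing about that person's platelet production. This requires baseline-relative scaling, strict linearity and last use in the narrow interval just outside the window, all together. The protocol states none of these and plans no classification of individuals, so the inference is not supported.
- **Practical weight.** The benchmark is itself only about 10%, so a mean of 10.1% to 10.5% would hardly change a pilot's conclusion. This is correct and sets the grade.

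None of these reconciles the written window with the stated duration of effect. They show that harm may not occur, not that the rule prevents it.

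**Conclusion.** The point holds and is minor. On the protocol's own figures, the aspirin exclusion can admit a volunteer whose only pre-aspirin sTxB2 is about 80% or 90% of true, or 70% if day 7 is eligible. The effect on the baseline summaries is direct: with an assumed 1 to 4 of 20 at day 8, the baseline mean reads 1% to 4% low. The effect on the recovery rate, 12.5% or 11.1% per day in an affected volunteer and about 10.1% to 10.5% for the group, depends on baseline-relative scaling.

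These sizes rest on linear recovery at 10% per day, no gap between enrolment and baseline, and an assumed number affected. The true number is unknown and may be zero. The point concerns aspirin only, since the protocol gives no duration of effect for the other listed drugs. An eligibility window belongs in the protocol, so this is not a matter left to the statistical analysis plan.

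**What to change.** Reconcile the aspirin window in the exclusion criteria with the duration of effect stated in Background and Rationale. Unless Figure 1 already fixes the interval from enrolment to baseline, count the window back from the baseline blood sample. No window length is proposed here; the investigators should set one that agrees with their own stated figures.

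The cost is one line in the eligibility criteria. A few volunteers with recent aspirin use may have to wait some days. No extra visits, samples or participants are needed, and if no volunteer has recent aspirin use there is no cost.

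### Does the plan leave out the spread of individual recovery rates by summarising serum TXB2 only at each time point?

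*Protocol*

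**What the plan says.** Under Statistical considerations, the Sample size bullet gives 20 participants on feasibility grounds: "As a pilot study, we plan to enroll 20 patients as recruitment of this number is feasible". It promises "estimates of mean/median and variability (e.g. standard deviation and range) of serum thromboxane B2 and recovery in healthy volunteers" and says that the study "will inform on sample size calculation of future studies with this assay".

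Two proposed analyses follow. The first is descriptive: "Biological variability of serum TXB2 will be represented as mean/median and standard deviation/range, at each time point of sampling". The second plots residual serum TXB2 against time, and the "recovery rate of serum TXB2 will be estimated, and compared with 10% rate of new platelet production reported in historic studies".

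The Study design section samples each volunteer before aspirin, then "at 4h after last dosing (daily peak level), and then daily for 5 days after aspirin cessation", which makes seven samples per person. The Specific objective makes the rate the quantity of interest: to show that "the recovery of their serum thromboxane B2 levels occurs at a rate of about 10% per day after aspirin cessation". The section on the role of the principal investigator assigns the writing of a detailed statistical analysis plan.

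**The concern.** Of the two quantities whose variability is promised, only the level has a standard deviation and range written into its analysis bullet. The recovery bullet names no standard deviation, range or interval, and does not say whether the rate is fitted per volunteer or to pooled data.

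Recovery is what the later programme would compare between groups. A cross-sectional standard deviation of levels mixes differences in people's absolute TXB2, true differences in recovery, day-to-day variation and assay error. If it were all the pilot delivered, a later study of recovery could be badly mis-sized and there would be no healthy spread to judge individuals against. A further irritation is that the protocol collects "3 ml of blood in EDTA for platelet count at baseline" but lists no analysis that uses it.

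**Working it through.** The figure of 20 rests on feasibility, with no alpha, power, effect size or standard deviation, so there is no calculation to reproduce. Every variance below is an assumption, because the protocol gives none.

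**1. The bullets side by side.**

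| Promised under Sample size | Matching proposed analysis |
|---|---|
| Centre and spread of serum TXB2 | First bullet: spread written out, per time point |
| Centre and spread of recovery | Second bullet: rate estimated and compared with 10%; spread not repeated |

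The second row is brief, not contradictory. The spread of recovery is already committed to in the same section, and nothing says that the first row replaces it.

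**2. Could time-point standard deviations alone supply the spread of recovery?** Not in general. For a least-squares slope over days 1-5, the sum of squares of time is 4 + 1 + 0 + 1 + 4 = 10. With a constant time-point SD *s* (points of baseline) and within-person correlation ρ, the SD of individual slopes is s√((1 − ρ)/10). With s = 10:

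- ρ = 0: 3.16 points/day
- ρ = 0.5: 2.24
- ρ = 0.8: 1.41
- ρ = 0.9: 1.00

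To detect 2 points/day between two groups (two-sided 5%, 80% power), n per group = 2(1.96 + 0.842)² × SD²/2² ≈ 3.92 × SD², giving 40, 20, 8 and 4. So an SD of individual rates is needed as well.

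If people differ in rate and start near zero, the SD grows with time. Taking 2, 4, 6, 8 and 10 points on days 1-5, the slope SD is 2.23 at ρ = 0 and 2.00 at ρ = 1, and n is 20 and 16. In that more natural pattern the ambiguity is small.

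**3. What would misuse of the time-point SD cost?** Assume a baseline CV of 30-50%, individual rates with mean 10 and SD 2 points/day (CV 20%), and 15% multiplicative error per sample.

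- Raw day-5 concentration: CV² = (1 + CV_b²)(1.04)(1.0225) − 1. For CV_b = 0.3, CV² = 0.159 (CV 40%). For CV_b = 0.5, CV² = 0.329 (CV 57%).
- Against the assumed true-rate CV² of 0.04, the ratios are 0.159/0.04 = 4.0 and 0.329/0.04 = 8.2. But 20% is the input, free of error. A later study would observe estimated slopes.
- Estimated slope, days 1-5: weights (−2, −1, 0, 1, 2)/10, and the sum of weight² × day² = (4 + 4 + 0 + 16 + 100)/100 = 1.24. Variance = 4 + 1.24 × 104 × 0.0225 = 6.90, so CV² = 0.069 (CV 26%). With 15% error in the baseline too, CV² = 1.069 × 1.0225 − 1 = 0.093 (CV 31%).
- Ratios against estimated slopes: from 0.159/0.093 = 1.7 to 0.329/0.069 = 4.8.
- Day-5 value as percent of own baseline: CV² = 1.04 × 1.0225 − 1 = 0.063 (CV 25%), or 0.087 (CV 30%) with baseline error. Ratios: 0.063/0.069 = 0.92 and 0.087/0.093 = 0.94. There is no inflation.

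**The case for a change.** The best case for a change is that this is more than omitted detail. The protocol does write out a variability analysis, and it writes it for the level, although the pilot's stated statistical purpose is to plan later studies and the rate is the readout of platelet production. One added clause would cost nothing, since the samples are already planned.

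Part of this stands. The recovery bullet is thin, and step 2 shows that time-point standard deviations do not in general determine the spread of slopes. In the other direction, the promise of a spread of recovery is explicit in the same section, and the second bullet does estimate recovery. Whether to use per-volunteer slopes or a random-slope model, and which interval to report, is commonly settled in the statistical analysis plan.

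Two side points do not stand. Seven single draws, taken in different states of inhibition, cannot separate assay error from day-to-day biology; that needs replicate assays. The baseline platelet count can simply describe the sample, and a missing listed use for it is not an error.

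**Conclusion.** No change is needed. Read together, the Sample size and Proposed analyses bullets already require the centre and spread of recovery, and the serial samples provide a rate for each of the 20 volunteers. An analyst following the text would fit those rates and report their mean or median, SD and range, with the volunteer as the unit. What is left unsaid is detail for the statistical analysis plan, which was not available here.

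The harm would arise only if a later planner applied the SD of raw concentrations to a recovery endpoint, which no passage proposes. Even then the inflation is about 1.7- to 4.8-fold on the assumed inputs, and it disappears when levels are expressed against each person's own baseline. Both results depend on the assumed baseline CV of 30-50%, rate SD of 2 points/day and 15% error. The conclusion that no change follows does not depend on them; it rests on the wording of the section.
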